#### **Resting Metabolic Rate**

The test will be aborted if the subject feels too claustrophobic to continue.

#### **BodPod**

Some subjects may find this procedure slightly claustrophobic. However, due to the short measurement time (less than 2 minutes total inside the BodPod), this risk is minimal.

#### **fMRI**

If the subject becomes too anxious during MR scanning, the session will be stopped. Subjects with claustrophobia and paramagnetic metal in the body will be excluded. In addition to the initial metal screening, subjects will fill out the standard MR screening form, which contains a detailed checklist to ensure subjects are free of paramagnetic metal, prior to scanning. This form will be reviewed by the MR technologist immediately prior to scanning.

#### **Blood Draw**

Using a phlebotomist with sufficient experience in hygiene practices and proper technique minimizes these risks.

#### **IV Catheter**

The risks are minimized by using highly trained staff.

#### **Confidentiality**

To address confidentiality risks, the research team will take great care in protecting participant confidentiality, by (1) storing all data in locked file cabinets in the PI's office (which is locked when unoccupied), (2) password-protecting all electronic data, (3) identifying all data by numerical code with no personal identifying information, and (4) restricting access to all data to the research team.

#### **D. Potential Scientific Problems:**

We felt that the proposed 12 weeks would be sufficiently long to detect effects on weight, in addition to neuronal effects, while minimizing dropouts that may occur with longer durations.

#### **F. Data Analysis Plan:**

A mixed model repeated measures analysis of variance will be used to assess group differences (DMXB-A vs. placebo) in intervention-associated change from baseline to post-intervention. Potential covariates will include age, sex, and DMXB-A plasma level. Missing data will be considered missing at random. Missing data generally occur from subjects who cannot complete one arm of the test or from a technical failure. fMRI data will be processed with Statistical Parametric Mapping (SPM12, Wellcome Trust Centre for Neuroimaging) in Matlab. All data initially will be visually inspected for motion, field homogeneity and reconstruction errors. Data from each participant will be realigned to the first volume, normalized to the Montreal Neurological Institute (MNI) template using a gray-matter-segmented IR-EPI as an intermediate to improve registration, and smoothed with an 8-mm full width at half maximum Gaussian kernel to improve signal to noise ratio and account for the non-independence on neighboring voxels. For the visual food-cue task, after preprocessing, a 128-second high-pass filter will be applied to remove low-frequency fluctuation in the BOLD signal. To account for both intersubject and intrasubject variability, a random effects statistical model will be utilized. To generate the random effects model in SPM8, statistical parametric maps will first be generated for each subject using the general linear model to describe the variability of the data on a voxel by voxel basis. The hemodynamic response will be modeled with a double gamma function, without

temporal derivatives. Because the first level analysis only considers a single source of error variance, in this case scan-to-scan residual error, a second level analysis will be performed to incorporate both within subject and between subject variance, thus allowing inference to the population. This will be accomplished by summarizing each individual subject's data with one parametric map (accounting for within subject variance), and then assessing these measures across subjects (accounting for between subject variance), thereby implementing a random effects model. Single subject SPM contrast images will be entered into a second-level repeated measures ANOVA in which contrasts of interest will be evaluated. For the resting state network analysis, group ICA analyses will then be performed using the GIFT toolbox (<http://icatb.sourceforge.net>). The dimensionality of the data from each subject first will be reduced using principle component analysis (PCA). Data sets will then be concatenated into an aggregate data set and the number of spatially independent sources will be estimated with a minimum description length (MDL) algorithm^66. The data will be further reduced to the number of independent components indicated by MDL. An independent component analysis (ICA) then will be performed using the infomax algorithm^67. Individual ICA maps will then be back-reconstructed. The default network component will be identified by selecting the independent component with the highest spatial correlation to a default network mask. This component will be entered into a second-level model in SPM12.

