### **IV. Research Methods**

#### **A. Outcome Measure(s):**

- a. Neuronal response to visual food cues
- b. Intrinsic resting state network activity (default network)
- c. Body weight and fat mass
- d. Appetite ratings

The primary outcome measure in this study is neuronal response, to both food cues and during rest.

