
#### **Intervention:**

Following baseline assessments, subjects will be randomized to DMXB-A or placebo in a 1:1 ratio. The randomization scheme will be prepared by a study biostatistician. Only the study pharmacy (Belmar Pharmacy) will be aware of drug assignment. They will have no direct interaction with study participants. A pharmacist at Belmar Pharmacy will dispense biweekly pill

vials to the study staff for distribution to subjects. Subjects will receive the drug for approximately 12 weeks, with biweekly visits (at weeks 2, 4, 6, 8, and 10; visits may be conducted remotely via phone or video call when possible) for pill box administration and side effect evaluation. The final pill capsule will be taken at the AMC on the morning of the post-intervention study visit, after the first blood draw. Women of child bearing potential will complete pregnancy tests as part of screening procedures, at baseline, and monthly throughout the study (weeks 4, 8, and 12). Blood tests (comprehensive metabolic panel, lipid panel, CBC, TSH, A1c and leptin) will be completed at screening. The comprehensive metabolic panel will be repeated at weeks 4, 8 and 12. The lipid panel and leptin will also be repeated at week 12. A blood draw will not be completed at the baseline study day, unless it has been more than 60 days since the screening day. This blood draw will measure the complete metabolic panel to reassess liver function. On the post-intervention study day, a nurse will insert an IV for blood draws in the morning. The initial blood draw will be used to measure DMXB-A levels, lipids, complete metabolic panel, and leptin. Three more blood draws will be completed on the post-intervention study day, each of which will be used to measure DMXB-A levels. If the nurse/phlebotomist has difficulty inserting the IV, a single blood draw for lipids, complete metabolic panel, and leptin will be considered acceptable. Each group will receive one capsule per day. The drug dose to be used for this study will be 50 mg, qd. The formulation will use a methylcellulose filler (Dow Chemicals) and be prepared by a compounding pharmacy. Placebo pills identical in appearance will be given to those in the placebo group.

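### Baseline adjustment is left unspecified in the two-visit change analysis; fixing it in advance is an optional gain in precision, not the correction of an error

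*Combined protocol and SAP*

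**What the plan says.** Section IV.F compares the arms with a repeated-measures mixed-model ANOVA that "will be used to assess group differences (DMXB-A vs. placebo) in intervention-associated change from baseline to post-intervention". On covariates it says: "Potential covariates will include age, sex, and DMXB-A plasma level". The outcome's own baseline value is not named, although the list is not stated to be closed.

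The primary outcome has two parts (section IV.A): "The primary outcome measure in this study is neuronal response, to both food cues and during rest". For the food-cue part, section IV.F says: "Single subject SPM contrast images will be entered into a second-level repeated measures ANOVA in which contrasts of interest will be evaluated". For the resting part, it selects "the independent component with the highest spatial correlation to a default network mask" and then says: "This component will be entered into a second-level model in SPM12". The design of that last model is not given. Nowhere are the arms set to a common baseline mean.

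There are two assessments, one before and one after treatment (section IV.C). The Intervention subsection says: "Following baseline assessments, subjects will be randomized to DMXB-A or placebo in a 1:1 ratio". On incomplete data, section IV.F says: "Missing data generally occur from subjects who cannot complete one arm of the test or from a technical failure".

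**The concern.** In a randomised trial with one baseline and one follow-up value, a comparison of mean change fixes the weight on baseline at exactly 1, whatever the data show. ANCOVA, or a mixed model that lets the arms share a baseline mean, uses the weight that the data support. A chance baseline imbalance is then neither over- nor under-corrected, and the treatment effect is estimated with less noise unless the best weight happens to be close to 1.

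Only precision is at stake. The listed outcomes are already measured before randomisation, so the information is in hand. The present wording also fits either a free-mean or a common-baseline model. If that choice is not fixed in advance, it could be made after the data are seen.

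**Working it through.** **Inputs.** From the documents: two visits, 1:1 allocation after baseline, a test of change between arms, no stated baseline term. The documents give no SD, sample size, dropout rate or baseline-to-week-12 correlation (rho), so there is no figure of the plan's own to reproduce. Everything below uses assumed values. Let k be the post-intervention SD divided by the baseline SD.

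**1. Validity.** In 20,000 simulated trials per setting (10, 20 or 30 per arm, rho 0.3 to 0.9), the change score was unbiased (mean estimate 0.496 to 0.506 for a true 0.5), with type I error 0.047 to 0.051. ANCOVA was also unbiased, with type I error 0.047 to 0.053.

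**2. Complete data, large samples.** With free baseline means, the group-by-visit test is the change-score test. In units of the baseline variance:

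- change score: 1 + k² − 2·rho·k
- baseline-adjusted: k²(1 − rho²)
- difference: (1 − rho·k)², which is never negative and is zero only when the optimal slope rho·k equals 1

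At k = 1 the ratio of adjusted to change-score variance is (1 + rho)/2. For example, rho 0.5 gives 1.5/2 = 0.75.

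| Variance ratio | rho 0.3 | 0.5 | 0.7 | 0.9 |
|---|---|---|---|---|
| k = 1 | 0.65 | 0.75 | 0.85 | 0.95 |
| k = 0.8 | 0.50 | 0.57 | 0.63 | 0.61 |
| k = 1.3 | 0.81 | 0.91 | 0.99 | 0.92 |

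**3. Missing data, k = 1, compared with the free-mean mixed model.** If a fraction m lacks only the post-intervention value, the ratio is (1 + rho)/[(1 + rho) + (1 − m)(1 − rho)]. With m = 0.2 and rho 0.5 this is 1.5/(1.5 + 0.4) = 0.79. Across the four correlations it is 0.70, 0.79, 0.88 and 0.96, the same for ANCOVA and the common-baseline model. A simulation with 20 per arm, 4 of them missing, gave a smaller gain: 0.72, 0.81, 0.91 and 0.99. With 5% lacking only baseline and 15% only follow-up, the common-baseline model gives 0.67, 0.76, 0.85 and 0.95 in large samples. Complete-case ANCOVA can then lose: at k = 1.3 and rho 0.7 its variance is 1.02 times that of the free-mean model, or 1.04 times with 10% and 10% missing.

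**4. Small samples.** Expected 95% interval width relative to the change score is the square root of the ratio in step 2 times a factor for estimating the slope and losing degrees of freedom. For baseline alone the factor is 1.033, 1.014 and 1.007 at total N of 20, 40 and 80. For three covariates it is 1.111, 1.045 and 1.020.

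| Width, k = 1, baseline only | rho 0.3 | 0.5 | 0.7 | 0.9 |
|---|---|---|---|---|
| N = 20 | 0.83 | 0.90 | 0.95 | 1.01 |
| N = 40 | 0.82 | 0.88 | 0.94 | 0.99 |

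Simulated widths agree. At k = 1.3 and rho 0.7, where the slope 0.91 is close to 1, the width is 1.03 at N = 20 and 1.01 at N = 40. At k = 1 the adjusted interval is narrower only below rho of about 0.87, 0.94 and 0.97 at N of 20, 40 and 80.

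**5. Power, illustration only.** Assume a difference of 0.5 SD, two-sided 5%, k = 1 and 30 per arm. By the normal approximation, power rises from 37% to 53% (rho 0.3), 49% to 61% (rho 0.5) and 71% to 77% (rho 0.7). Simulation at rho 0.5 gave 48% to 59%.

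**6. Age and sex.** In 500 simulated complete data sets of 40 subjects, adding them as main effects left the group-by-visit estimate unchanged apart from rounding. They help that comparison only if they act on the follow-up value.

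**The case against.** The strongest reply is that nothing here is wrong. The planned test is valid, change score versus ANCOVA is a matter of choice, and a mixed model with an open covariate list may already be meant to share a baseline mean. Since the resting-state model is not described, no loss can be shown there. All of this stands. It is why the point is optional, but a sentence naming the model is still needed.

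A second reply is that the sizes are all assumed and may be small. The large-sample complete-data ratios run from 0.50 to 0.99, and the gain is about nil at very high rho, as is likely for body weight. If age and sex are also entered and predict nothing, the three-covariate factors put break-even at rho of about 0.62 for N = 20 (2/1.111² − 1) and 0.83 for N = 40 (2/1.045² − 1). At N = 20 and rho 0.7 the interval is then about 2% wider than with the change score (0.922 × 1.111 = 1.02). That stands too, though most of this cost comes from age and sex, not from baseline.

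The third reply has most force. The primary analysis is voxelwise, and a different covariate at each voxel is not part of the workflow described. A regional summary would change the endpoint from a map to a number, and the mask is now used only to pick a component. If both visits enter the group ICA together, which the plan does not say, the baseline map also depends on follow-up data. The change is therefore cheap for scalar outcomes and less so for the maps. The ICA point applies equally to a change score built from those maps.

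**Conclusion.** The concern holds as an optional improvement. The plan neither adjusts for baseline nor sets a common baseline mean, and read with free baseline means it gives up some precision without gaining validity. At equal SDs the large-sample variance saving is (1 − rho)/2: 35% at rho 0.3, 25% at 0.5, 15% at 0.7 and 5% at 0.9. It is worth having if the imaging and appetite measures have low to moderate correlation over 12 weeks, and negligible if rho is near 1. In small trials the baseline covariate alone can widen the interval by about 1 to 3% when rho is high or the optimal slope is near 1. These sizes rest on assumed correlations, SDs, sample sizes and missingness. The use of drug plasma level as a covariate is a separate question that this point does not cover.

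**What to change.** For each outcome, state one of two models in advance: ANCOVA on the post-intervention value with its own baseline as covariate, or a two-visit mixed model with a common baseline mean. If only follow-up values are missing, both give the same maximum-likelihood treatment estimate. Where a baseline can be missing, for example after a technical failure, the common-baseline model is the safer choice because complete-case ANCOVA drops those subjects.

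- **fMRI:** use the baseline value of the same contrast (fasted, fed, or fed minus fasted), either as a voxelwise covariate or in a pre-specified summary. The default network mask could supply the resting-state summary. No region is named for the food-cue task, so one would have to be named first. State also whether the group ICA pools both visits.
- **Appetite:** choose one per-visit summary of the six post-meal ratings and adjust for that same summary at baseline.
- **Age and sex:** decide beforehand whether they are used. If so, enter them as ANCOVA covariates or as age-by-visit and sex-by-visit terms.

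The cost is SAP wording, one degree of freedom for baseline and one for each further covariate, plus a script if the voxelwise route is taken. No new data are needed. With baseline, age and sex all entered, and age and sex predicting nothing, the widening factor is about 11% at N = 20 and 4.5% at N = 40, before any gain from baseline.

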#### **C. Study Design and Research Methods**

Participants will complete two study phase assessments: (1) at baseline and (2) post-intervention.

**Study Phase Assessments:** The following evaluations will be completed during both study phases: After a 1-day run-in eucaloric diet period to ensure energy and macronutrient balance, subjects will arrive the morning after an overnight fast. Prior to each study phase assessment day, participants will wear an activity monitor for 5-7 days (ActivPal, Glasgow, Scotland), to assess any activity differences between groups. Sleep habits will be assessed via brief self-report questionnaire (Pittsburgh Sleep Quality Index; PSQI) at both assessment days to determine if group differences in sleep habits are a possible confounding variable. A blood draw will not be completed at the baseline study day, unless it has been more than 60 days since the screening day. This blood draw will measure the complete metabolic panel to reassess liver function (i.e., we will not repeat all screening blood labs, only the complete metabolic panel). On the post-intervention study day, a nurse will insert an IV for blood draws in the morning. The initial blood draw will be used to measure DMXB-A levels, lipids, complete metabolic panel, and leptin. Three more blood draws will be completed on the post-intervention study day, each of which will be used to measure DMXB-A levels. If the nurse/phlebotomist has difficulty inserting the IV, a single blood draw for lipids, complete metabolic panel, and leptin will be considered acceptable. Following the first blood draw on the post-intervention study day, subjects will take their final pill capsule, prior to completing any other study measures. The remaining three blood draws will be taken approximately 1 hour after taking the pill, 2 hours after taking the pill, and 6 hours after taking the pill. During both study days, subjects will complete assessments of body composition, food and eating-related behaviors (Three Factor Eating Questionnaire (TFEQ); Power of Food Scale; Food Craving Inventory), cognitive and mood measures (Digit Span task; Coding task; Comprehensive Trail Making Test [CTMT]; Center for Epidemiological Studies Depression Scale (CES-D); State Trait Anxiety Index [STAI]), and appetite evaluations (hunger, appetite, satiety). Following these measures, subjects will be escorted to the Brain Imaging Center for fMRI measures (visual food cue task and resting-state), which will first be performed in the fasted state, then again in the fed state (approximately 30 minutes following a breakfast meal, described below). Appetite evaluations will be performed at approximately 30, 90, 120, 150, 180, and 210 minutes post-meal. Subjects may then complete a measure of resting metabolic rate, followed by a buffet-style lunch at the Anschutz Health and Wellness Center to measure ad libitum food intake.

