
**Run-In Diet:** A 1-day eucaloric, run-in diet will be performed prior to the study day during each of the study phase assessments. The caloric value of the diet will be determined by taking into account age, gender and weight, adjusted for physical activity, and will have a macronutrient composition of approximately 50% carbohydrate, 30% fat, and 20% protein. This approach has been used effectively by our group in a number of prior studies. All meals will be prepared by the metabolic kitchen of the Anschutz Health and Wellness Center (AHWC) or the CTRC. Subjects will report to the AHWC or CTRC in the morning, be weighed, eat breakfast on the unit, and pick up food for the remaining meals (lunch, dinner, snack). Subjects will be asked to return containers and uneaten food from the previous day when they arrive the next day for the study day. Subjects will be asked to not consume any other food or beverages and to maintain usual activities.

**Resting Metabolic Rate (RMR):** After approximately 30 minutes of quiet rest, RMR may be measured prior to lunch on each study day, using standard indirect calorimetry with the ventilated hood technique (Parvo Medics Truemax 2400). It is acceptable to omit this measure if data cannot be collected in accordance with COVID-19-related University and CTRC guidelines, or if participants/staff feel it would be safer to omit it.

**Body Composition:** Body composition will be measured using BOD POD air displacement plethysmography (Life Measurement, Inc., Concord, CA) at baseline and after the intervention. This measure takes approximately 2 minutes to complete.

**Blood Analyses:** Blood analyses will take place as follows (also see study procedures table, p.7): Complete metabolic panel at screening and at weeks 4, 8 and 12. Lipid panel and leptin at screening and week 12. CBC, TSH, A1c, and cotinine at screening. At the post-intervention study day (week 12 visit), we will utilize an IV catheter to facilitate 4 separate blood draws to measure DMXB-A blood levels. These draws will take place immediately prior to morning study drug dosing, and approximately 1 hour post-dose, 2 hours post-dose and 6 hours post-dose. If the nurse/phlebotomist has difficulty inserting the IV, a single blood draw for lipids, complete metabolic panel, and leptin will be considered acceptable.

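### Post-randomisation DMXB-A plasma level is a potential covariate in the DMXB-A versus placebo model, where common codings change what the group term estimates

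*Combined protocol and SAP*

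**What the plan says.** Section F (Data Analysis Plan) names a repeated-measures mixed model that "will be used to assess group differences (DMXB-A vs. placebo) in intervention-associated change from baseline to post-intervention". The next sentence reads: "Potential covariates will include age, sex, and DMXB-A plasma level".

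The timing is explicit elsewhere:

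- **Randomisation.** Under Intervention: "Following baseline assessments, subjects will be randomized to DMXB-A or placebo in a 1:1 ratio".
- **Plasma level.** It is measured only on the post-intervention day. The first draw includes it, and section C continues: "Three more blood draws will be completed on the post-intervention study day, each of which will be used to measure DMXB-A levels". The Blood Analyses paragraph in section D gives the times: "These draws will take place immediately prior to morning study drug dosing, and approximately 1 hour post-dose, 2 hours post-dose and 6 hours post-dose". Any baseline draw happens only if more than 60 days have passed since screening, and then covers the metabolic panel alone.
- **Treatment.** "The drug dose to be used for this study will be 50 mg, qd". For the control arm: "Placebo pills identical in appearance will be given to those in the placebo group".
- **Fallback.** If the IV cannot be placed, "a single blood draw for lipids, complete metabolic panel, and leptin will be considered acceptable". No DMXB-A assay is listed for that draw.

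The plan does not say which of the four draws (or which summary of them) is the covariate, how it is coded or centred, or whether it interacts with time. It does not restrict it to an exploratory or active-arm analysis. The second-level imaging models in the same section name no covariates.

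**The concern.** A covariate in a randomised comparison should not be affected by treatment. Drug level is created by treatment. The documents do not state the placebo value, but a placebo capsule contains no DMXB-A, so it should be zero or a constant at the assay limit. The slope on level can then be estimated only in the DMXB-A arm, and the model uses it to project that arm back to the placebo value.

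What this does depends on which situation holds:

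1. If the effect runs through exposure, that part is taken out of the group term.
2. If a prognostic factor also drives level, a false group effect can appear when the drug does nothing. Body size and adherence are candidates by inference: everyone gets the same dose, the weight range is wide (the stated limit is 500 lb), and pills are counted.
3. If the effect does not depend on level, the estimate stays unbiased but loses precision.

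At stake are outcomes analysed with this model, such as body weight, fat mass and appetite ratings. Because inclusion and coding are both open, the same data could give materially different group estimates. Participants without a level could also drop out of a model that needs one.

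**Working it through.** The available text gives no sample size, effect size or level variability, so there is no figure of the plan's own to reproduce. All numerical inputs below are assumptions.

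**Step 1: what the group term estimates.** Let G = 1 on DMXB-A and 0 on placebo, and let C be level, with C = 0 on placebo. Fit change = b0 + b1·G + b2·C. Since C does not vary on placebo, b2 is the slope within the DMXB-A arm, and

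b1 = (mean change on DMXB-A − mean change on placebo) − b2 × (mean level on DMXB-A).

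This is the DMXB-A regression line at C = 0 minus the placebo mean. Direct calculation confirmed the identity to about 1e-14. Subtracting the grand mean from C changes only b0, so b1 is the same. A group-by-level term cannot be added, because the design then has rank 3 of 4.

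If a share s of a true effect D is proportional to level, b2 × mean level = s·D, so b1 = (1 − s)·D. For D = 0.8 SD this gives 0.80, 0.40 and 0 at s = 0, 0.5 and 1.

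**Step 2: loss of precision.** Scale mean level to 1 and let c be its coefficient of variation (CV) on DMXB-A. With 1:1 allocation, Var(G) = 1/4, Cov(G,C) = 1/2 − 1/4 = 1/4, and Var(C) = (1 + c²)/2 − 1/4 = 1/4 + c²/2. So corr² = 1/(1 + 2c²), and the variance inflation is 1/(1 − corr²) = 1 + 1/(2c²):

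- c = 30%: 1 + 1/0.18 = 6.6
- c = 50%: 1 + 1/0.50 = 3.0
- c = 100%: 1 + 1/2 = 1.5

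**Step 3: false effect with an inactive drug.** Let r be the correlation on DMXB-A between level and change not caused by the drug. With the SD of change set to 1, the slope is r/c and the group term is about −r/c. For r = 0.25: −0.83, −0.50 and −0.25 at c = 30, 50 and 100%.

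**Step 4: simulation.** Least squares on change, 4000 trials per setting, 30 per arm, lognormal level, two-sided 5%. Figures separated by slashes are for c = 30/50/100%.

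| True state | Without level: rejection | Raw or grand-mean-centred: estimate | Raw or grand-mean-centred: rejection |
|---|---|---|---|
| 0.8 SD, all proportional to level | 85/84/77% | about 0.00 | 4-5% |
| 0.8 SD, half proportional | 83-86% | 0.38-0.40 | 8/14/21% |
| 0.8 SD, independent of level | 86-87% | 0.78-0.82 | 20/41/64% |
| No effect, r about 0.25 | 4-5% | −0.85/−0.51/−0.25 | 23/18/11% |

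With level centred within arm, the estimate stays at 0.80 in the first row, and type I error is 4-6%. Over r from about 0.09 to 0.35, type I error under the harmful codings runs from 6 to 39%. At r about 0.25 it is 16/13/9% with 20 per arm and 36/28/17% with 50 per arm. In these runs r was set through log level; on the raw scale the nominal 0.25 is 0.245/0.236/0.208.

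**Step 5: the mixed model itself.** Two-visit REML fits, 40 trials, 30 per arm, c = 50%, effect proportional to level. Mean group-by-time estimate:

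- no level: 0.77
- level as a time-constant main effect: 0.77 (largest difference 2.0e-15)
- level centred within arm, by time: 0.77 (largest difference 1.3e-15)
- raw level by time: 0.03
- grand-mean-centred level by time: 0.03
- time-varying level: 0.01

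So harm requires that level act on change. With complete data, the time-constant main effect and within-arm centring leave the contrast unchanged.

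**The case against.** The strongest reply is that the plan commits to nothing. Level is only a potential covariate, no coding is given, and in a repeated-measures model a plain main effect does no harm. That is correct and limits the point to an option the plan leaves open. It is still a named option in the group comparison, and some ordinary codings of it give a wrong group estimate.

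Four further points deserve weight.

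- **Reach.** Neuronal response is primary, and no covariates are named for the second-level imaging models. This stands: harm to the primary outcome is not shown.
- **Drivers of level.** The final capsule is taken on site after the first draw, so the three later draws follow a dose given at the visit. Only the pre-dose draw rests solely on earlier pill-taking, which weakens adherence as a driver. The 500 lb limit is a scanner limit and not exposure data. Both remain candidates only.
- **Assumed magnitude.** This stands. The rates above are illustrations, and at the low end of r the type I error is near nominal.
- **Within-arm centring.** It left the estimate unchanged and gave higher power at CV 100% (83% against 77%). That gain comes from a smaller standard error on the same estimate, with interval coverage of about 90%, so it is no reason to keep level in the comparison.

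No IV failure rate is given, so loss of participants through missing levels is a possibility of unknown size.

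**Conclusion.** The concern holds. That level is measured after randomisation is stated in the documents; that it is zero or constant on placebo is an inference, though a safe one. Given both, the change in what the group term estimates is algebra and does not depend on the simulation inputs. It applies when level enters raw or grand-mean-centred so that it acts on change: in a change-score model, by time, or as a time-varying covariate.

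The size does depend on assumptions about sample size, effect, CV of level, correlation and the share of effect running through level. Within the ranges examined, a real effect can be reduced to about zero or a false one produced at more than twice the nominal rate. Confidence in the mechanism is high. Because the covariate is optional and correction costs nothing, this is best treated as a free improvement.

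**What to change.** Replace the covariate sentence in section F with:

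> Any covariates in DMXB-A versus placebo comparisons will be limited to variables recorded before randomisation (such as age and sex). DMXB-A plasma level will not enter any DMXB-A versus placebo comparison. It will be used only in an exploratory exposure-response analysis within the DMXB-A arm, using one summary of the week-12 draws named in advance.

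The planned checks for group differences in sleep and activity are unaffected. Under this wording, post-intervention sleep or activity would not be used as covariates in the group comparison. If the sponsor wants the narrowest change, the second and third sentences alone deal with plasma level.

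The cost is a wording change and one decision on how to summarise the four draws. No new data or visits are needed, and the exposure-response question is kept.
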